10.3 Demographic and Other Baseline Characteristics

10.3.1 Demographic and Baseline Data

Demographic and baseline data will be collected at Visit 1. The following data will be collected:

- Date of birth
- Weight and height

10.3.2 Medical History

For the documentation of the medical history, **relevant** previous and concomitant diseases, allergies and familiar predispositions during the last year before the screening will be documented in the source data and the eCRF.

The medical history will be obtained by asking the subject and by inspecting his/her medical records. Relevant medical and surgical history will be recorded at visit 1.

10.3.3 Prior Medication

Any medication taken by a subject within 12 month before the clinical trial is considered as prior medication.

Use of prior medication will be recorded in the source data and the eCRF at Visit 1.

10.3.4 Concomitant Medication

Any medication taken by a subject during the clinical trial apart from the trial medication is considered as concomitant medication.

Use of concomitant medication will be recorded in the source data and the eCRF at Visit 1 and during the whole trial period if changed.

10.4 Safety Assessments

10.4.1 Safety Variables

The following safety variables will be measured:

- Adverse Events (nature and incidence) (see Section 11.2)
- Physical examination
- Vital signs (blood pressure [11], heart rate and body temperature) in sitting position
- Laboratory safety assessments (haematology, clinical chemistry and urinalysis)
- Local tolerability, as defined in section 10.4.6

All local tolerability assessments must be performed by an investigator with dermatological expertise. As far as possible the same investigator shall assess a subject at all assessment. Safety of the IP after the first application of the single dose will be assessed by AE documentation approximately 15 minutes after injection, as well as throughout the whole trial. The assessing investigator will be identified in the source data at each visit.

10.4.2 Adverse Events

AEs will be recorded at Visit 1 and until the End of Trial.

For further information of definitions and reporting of AEs and SAEs, see Section 10.5.

10.4.3 Physical Examination

Standard physical examinations will be performed at Screening, Visits 0, 36 and EoT visit.

The physical examination will include:

- General appearance
- mouth and throat
- ears (left and right)
- heart
- lungs
- abdomen
- neurological (rough inspection of strength and touch sensation)
- axillary and inguinal lymph node palpation

The parameters will be assessed as "normal" or "abnormal". Abnormal findings will be specified and assessed as "clinically significant" or "not clinically significant".

Clinically significant abnormal findings at Visit 0 will be recorded in the source data and on the medical and surgical history page in the eCRF. New or worsening clinically significant abnormal findings at all subsequent visits will be recorded in the source data and on the AE page in the eCRF.

10.4.4 Vital Signs

Vital signs will be recorded at screening, visit 1, visit 36 and EoT visit. The following vital signs will be monitored as safety variables in a comfortable seated individual after 5 minutes:

- Supine systolic and diastolic blood pressure (mmHg)
- Supine heart rate (beats per minute)

• Body temperature measured in degrees Celsius (°C) according to site specific methods

The observed values will be recorded and assessed as "normal" or "abnormal". Abnormal findings will be assessed as "clinically significant" or "not clinically significant".

Clinically significant abnormal findings at Visit 1 will be recorded in the source data and on the medical and surgical history page in the eCRF. New or worsening clinically significant abnormal findings at all subsequent visits will be recorded in the source data and on the AE page in the eCRF.

10.4.5 Laboratory Assessments

A safety screen including standard safety laboratory parameters will be performed. Blood and urine samples for clinical chemistry and haematology evaluations will be collected at screening, 36 and at EoT visit. Serology samples will be taken at the screening visit and the result should be available at visit 1 before inclusion and randomisation. The samples will be analysed at the central laboratory LKF - Laboratorium für Klinische Forschung GmbH, Schwentinental, Germany.

The observed values will be recorded and assessed as "normal" or "abnormal". Abnormal findings will be assessed as "clinically significant" or "not clinically significant".

Clinically significant abnormal findings at Visit 1 will be recorded in the source data and on the medical and surgical history page in the eCRF. New or worsening clinically significant abnormal findings at following visits will be recorded in the source data and on the AE page in the eCRF.

The following laboratory parameters will be measured (Table 2):

Category	Laboratory Parameter
Haematology	haemoglobin, white blood cell count including differential cell count, red blood cell count, platelet count, coagulation (partial thromboplastin time and prothrombin time)
Clinical Chemistry	Glucose (random), creatinine, total bilirubin, gamma-
(blood serum)	dehydrogenase (LDH), total cholesterol
Urinalysis	blood, ketones, glucose, protein, pH, nitrites, leucocytes, microscopy if results are positive for blood or protein
Serology (at Screening visits only)	Hepatitis B (HBsAg, HB core antibody), hepatitis C, and HIV (anti-HIV).

Table 2Laboratory parameters

10.4.6 Local tolerability

At each visit, the investigator will assess the local tolerability using a 4-point local tolerability / safety assessment scale (Table 3).

Local Tolerability will be reported as an AE if the local tolerability signs and/or symptoms results in temporarily or permanently stopping of further administration of trial treatment or if it is stopped at the request of the subject.

The outcome will have to be followed until resolution, steady state or until evidence that the investigational products and/or the subject's participation in the trial are not responsible for the event.

ERYTHEMA						
SCORE	GRADE	DESCRIPTION				
0	None	No evidence of erythema present				
1	Mild	Slight pink discoloration				
2	Moderate	Definite redness, easily recognized				
3	Severe	Marked erythema, bright red to dusky dark red in color				
НАЕМАТОМА						
SCORE	GRADE	DESCRIPTION				
0	None	No haematoma				
1	Mild	Slight haematoma inside the treatment area				
2	Moderate	Definite haematoma of strong color inside the treatment area				
3	Severe	Marked haematoma, covering the whole treatment area				
DYSPIGMEN	TATION (HYPER-	AND HYPOPIGMENTATION)				
SCORE	GRADE	DESCRIPTION				
0	None	No signs of dyspigmentation				
1	Mild	Slight dyspigmentation of small definite area				
2	Moderate	Marked dyspigmentation inside the treatment area				
3	Severe	Dyspigmentation of the treatment area including areas not injected				
INDURATION	4					
SCORE	GRADE	DESCRIPTION				
0	None	No induration				
1	Mild	Barely perceptible induration				
2	Moderate	Induration palpable				
3	Severe	Marked induration				
PAIN/ DISCO	PAIN/ DISCOMFORT					
SCORE	GRADE	DESCRIPTION				
0	None	No pain or discomfort				
1	Mild	Slight pain, not really bothersome				
2	Moderate	Definite pain that is somewhat bothersome				
3	Severe	Intense pain that may interrupt daily activities and/or pain				
		Strong paraesthesia of the treatment area				

For subjective scoring, the subject should be questioned with regard to the period after the last and prior to the next injection procedures scheduled for the respective day.

10.5 Procedures

10.5.1 Screening period (Day -21 to -1)

Within the three weeks prior to the first visit, the volunteers will come to the sites for the initial screening (including documentation of demographic data). Screening assessments will be performed after the volunteer has agreed to participate and has signed and dated the informed consent form.

The following examinations will be performed:

- Documentation of relevant relevant medical and surgical history (last 1 year)
- Documentation of demographic data;
- Documentation of relevant previous medication (last 12 months);
- Check in-/exclusion criteria (see section 8.2 and 8.4);
- Physical examination of general appearance, mouth and throat, ears (left and right), lungs, abdomen, neurological (see section 10.4.3);

- Vital signs: systolic and diastolic blood pressure (mmHg), heart rate (beats per minute), and body temperature (see section10.4.4);
- Blood and urine sampling for assessment of safety laboratory parameters, HIV/hepatitis;
- Determination of treatment areas;
- Marking of test areas;
- Shaving of test areas;
- Tatooing of test area;

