The trial period will consist of a screening period of up to 1 week followed by 12 weeks of dosing, three times per week. Each subject will receive two doses of the four trial treatment doses (0.00625, 0.025, 0.050, and $0.100 \mu g$ respectively) and the placebo dose. On each volunteer, two treatment areas will be selected on the head and the two selected doses will be allocated to the respective treatment areas according to the randomisation scheme. The treatment areas will be selected on the border between the bald surface and the surface with hair.

The subjects will be screened for eligibility at the screening visit where a physical examination and assessment of vital signs will be performed. Blood samples for safety and laboratory assessment will be taken. The subjects will return to the clinic for the inclusion visit (visit 1, day 1) 3 to 21 days later. If the subject is eligible for inclusion, the 2 treatment areas will be shaved and the centre of each treatment area where the trial treatments will be applied will be marked with a tattooed dot.

At visit 2, day 5, the first trial treatment application will be performed after TrichoScan imaging of the treatment areas. Subjects will then return to the clinic for treatment application three times per week with at least one day in between.

All subjects who have received at least one dose of trial drug will go through the procedures for safety and efficacy assessments at last visit (EOT, visit 38).

All adverse events will be followed until resolved or stabilised. Procedures for removal of subjects from therapy or assessments are described in Section 8.7.

Number of subjects:

A total of 60 healthy male subjects will be included.

Each subject will be treated at two sites. Each site will be treated with different treatments.

Thus, a total of 120 treatment areas will be available for treatment on the 60 subjects

Inclusion criteria:

The subjects must meet all of the following criteria to be eligible to enter the trial:

- 1. Healthy male, aged 18-55 years
- 2. Androgenetic alopecia (AGA)) Norwood/Hamilton grade 3V to 4/4a [1]
- 3. Caucasian, skin type I IV according to Fitzpatrick's classification [2]
- 4. Willing to have treatment areas shaved for TrichoScan® measurement marked with small semi-permanent dot tattoos
- 5. Willing and able to comply with scheduled visits
- 6. Willing to maintain the same hygiene products and skin cleansing habits during the trial period.

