7 INVESTIGATIONAL PLAN

7.1 Trial Design and Plan-Description

The trial is a multicentre, randomized, double-blind, placebo controlled phase 2 trial.

The trial centres will screen a sufficient number of subjects (approximately n = 90) to include 60 eligible male subjects. Subjects withdrawn for IMP-unrelated reasons will be replaced if treatment was performed for less than 4 weeks.

60 healthy male subjects, who are 18 to 55 years old and provide written informed consent will be included

The trial period will consist of a screening period of up to 3 weeks followed by 12 weeks of dosing. Each subject will receive their first doses at visit 2 (day 5). Subjects will then return to the clinic for treatment application 3 times per week with at least one day in between. 4 active dose strengths and one placebo dose will be used in the trial and each subject will be randomly assigned two of these 5 treatments. Thus, all 60 subjects will receive 2 doses.

The subjects will be screened for eligibility at the screening visit where a physical examination and assessment of vital signs will be performed. Blood samples for HIV/Hep-b/Hep-c, safety and laboratory assessment will be taken. The subjects will return to the clinic for the inclusion visit (visit 1, day 1) 3 to 21 days later. If the subject is eligible for inclusion, the 2 treatment areas will be shaved and the centre of each treatment area where the trial treatments will be applied will be marked with a tattooed dot.

At visit 2, day 3, the first TrichoScan imaging of dyed hair for determination of baseline total hair density per cm² and the first trial treatment application will be performed on the treatment areas. Subjects will then return to the clinic for treatment application three times per week with at least one day in between.

All subjects who have at least received one dose of trial drug will go through the procedures at the Follow up safety and efficacy assessments at the EoT visit.

All adverse events will be followed until resolved or stabilised. Procedures for removal of subjects from therapy or assessments are described in Section 8.7.

Trial Treatments

 $50 \ \mu$ I of the trial treatments will be applied intradermally at each treatment site in the centre marked with a tattooed dot. The dilutions and preparation of vials will be performed at the centre, by blinded personnel.

The trial treatments will consist of three times per week application of:

- FOL-005 0.00625 µg solution, or

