10.2.2 Methods for Efficacy Assessments: TrichoScan imaging and measurement

10.2.2.1 Determination of Clinical Response to Investigational Product

Photos of the treatment areas will be taken, and assessment of hair growth (hair count and hair density) calculated based on TrichoScan images. The analysis of the images will be performed centrally by a unit independent of the investigators. The analysis of the images will be performed while keeping the blind with regard to the treatment assignment. Assessment of hair growth will be performed as follows:

At Screening:

- 1. Treatment areas will be trimmed over a large area to achieve a hair length of 1mm;
- 2. Treatment areas (1.5 cm in diameter) will be selected and marked by a dot tattoo;

At visit 1 (day 1):

- 1. Selected treatment areas (1.5 cm in diameter) will be identified;
- 2. Selected treatment areas will be trimmed over a large area to achieve a hair length of 1mm;
- 3. A TrichoScan image is taken without hair dye with the TrichoScan camera/optics system held always in the same position;

At visit 2 (day 3):

- 1. Selected treatment areas (1.5 cm in diameter) will be identified;
- 2. A TrichoScan image is taken after hair dye with the TrichoScan camera/optics system held always in the same position **prior to IMP treatment**;

The procedures of visit 1 are repeated for visits 23 and 35. The procedures for visit 2 are repeated for visits 24 and 36.

For details of the TrichoScan imaging please refer to the TrichoScan manual.

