10.5.2 Experimental phase

Visit 1

- Re-check of the inclusion and exclusion criteria (see section 8.2 and 8.4);
- Physical examination (see section 10.4.3);
- Vital signs (see section 10.4.4);
- Documentation of demographic data;
- Update of previous and concomitant medication;
- Recording of AEs/SAEs;
- Identification of treatment areas;
- Marking of test areas;
- Shaving of test areas;
- TrichoScan imaging without hair dye;
- Safety assessment and local tolerance assessment (see section 10.4);

Visit 2

- Update of previous and concomitant medication;
- Recording of AEs/SAEs (record potential AEs also 15 min after first application);
- Safety assessment and local tolerance assessment (see section 10.4);
- Randomisation
- Identification of selected treatment areas;
- Marking of selected treatment areas;
- TrichoScan imaging including hair dye
- IP application

Visit 3 - 21

- Update of previous and concomitant medication;
- Recording of AEs/SAEs;
- Safety assessment and local tolerance assessment (see section 10.4);
- Optinal: repeat of tattooing, if necessary;
- Identification of selected treatment areas;
- IP application

Visit 22

- Update of previous and concomitant medication;
- Recording of AEs/SAEs;
- Safety assessment and local tolerance assessment (see section 10.4);
- Identification of selected treatment areas;
- IP application

Visit 23

- Update of previous and concomitant medication;
- Recording of AEs/SAEs;
- Safety assessment and local tolerance assessment (see section 10.4);
- Identification of selected treatment areas;
- Marking of selected treatment areas;
- Shaving ot test areas
- TrichoScan Image without hair dye

Visit 24

- Update of previous and concomitant medication;
- Recording of AEs/SAEs;
- Safety assessment and local tolerance assessment (see section 10.4);
- Identification of selected treatment areas;
- Marking of selected treatment areas;
- TrichoScan imaging including hair dye
- IP application

Visit 25 - 36

- Update of previous and concomitant medication;
- Recording of AEs/SAEs;
- Safety assessment and local tolerance assessment (see section 10.4);
- Optinal: repeat of tattooing, if necessary;
- Identification of selected treatment areas;
- IP application

Visit 37

- Update of previous and concomitant medication;
- Recording of AEs/SAEs;

- Safety assessment and local tolerance assessment (see section 10.4);
- Identification of selected treatment areas
- Shaving ot test areas;
- TrichoScan imaging without hair dye;

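### The dot tattoo is placed both at screening and at visit 1, and under the screening order adverse event recording starts after the tattoo

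*Combined protocol and SAP*

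**What the plan says.** The protocol gives two times for the tattoo that marks the centre of each treatment area.

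- **Screening.** The list of screening procedures in 10.5.1 ends with "Tatooing of test area". Section 10.2.2.1, under its screening step, says "Treatment areas (1.5 cm in diameter) will be selected and marked by a dot tattoo". The flow chart (1.1 and Table 1) has its tattoo entry in the screening column and none at visits 1 or 2, with optional repeats later. The visit 1 lists in 10.2.2.1 and 10.5.2 contain no tattoo.
- **Visit 1.** The synopsis and 7.1 say "The subjects will return to the clinic for the inclusion visit (visit 1, day 1) 3 to 21 days later". They continue "If the subject is eligible for inclusion, the 2 treatment areas will be shaved", and the same sentence adds that the centre of each area where "the trial treatments will be applied will be marked with a tattooed dot".

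On adverse events, 10.4.2 and the flow chart start recording at visit 1. Section 11.2 starts it at the first dose. Section 11.1.1 defines an adverse event in terms of a subject who has been given a medicinal product. The screening list in 10.5.1 has no adverse event item. Section 11.3 requires serious events to be reported and names no start date.

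On the tattoo itself, 5.2 says that contact eczema from the dye appears within hours or days and often needs topical treatment.

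**The concern.** A site cannot follow both instructions. The eligibility condition appears only in the synopsis and 7.1, not in the sections a site works from visit by visit.

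If the site follows those operational sections, an invasive marking is made before all eligibility results need be known. The reaction that the protocol itself foresees can then arise before any adverse event recording is scheduled. A man who reacts may also become ineligible, through exclusion 26 (hypersensitivity to tattoo ink) or, if he is treated on the scalp, exclusion 11 (recent topical scalp treatment). Some of the men most affected might therefore never enter the study record as adverse event cases.

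What is at stake is completeness of procedural safety data and clear instructions to sites. The efficacy comparison is not involved.

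**Working it through.** The plan states no figure on this point. The check sets the sections side by side and counts days.

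**1. Where the tattoo falls**

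| Place | Time of tattoo | Conditional on eligibility? |
|---|---|---|
| 10.5.1 | Screening | Not stated |
| 10.2.2.1 | Screening | Not stated |
| Flow chart (1.1, Table 1) | Screening | Not stated |
| Synopsis | Visit 1 | Yes |
| 7.1 | Visit 1 | Yes |

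Section 10.5.1 lists an eligibility check ahead of the tattoo but does not make the tattoo depend on it. Section 10.4.5 needs serology results only by visit 1, so exclusion 20 can still be open when the tattoo is made. Section 10.5.2 repeats the eligibility check at visit 1.

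**2. Time from tattoo to start of recording**

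Inputs: visit 1 is day 1 and follows screening by 3 to 21 days (synopsis, 7.1). First dosing at visit 2 is day 3 in the flow chart and day 5 in the synopsis; 7.1 gives both.

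Tattoo at screening:

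- Recording from visit 1 (10.4.2, flow chart): 3 to 21 days.
- Recording from first dose on day 3 (11.2): 3 + 2 = 5 to 21 + 2 = 23 days.
- Recording from first dose on day 5 (11.2): 3 + 4 = 7 to 21 + 4 = 25 days.

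The heading of 10.5.1 (day -21 to -1) would allow a shortest interval to visit 1 of 1 day, counting no day 0.

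Tattoo at visit 1: no gap under 10.4.2, and 2 to 4 days under 11.2.

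An onset of hours or days therefore falls largely or wholly before recording starts under the screening order.

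**3. What visit 1 can still capture**

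Section 10.5.2 schedules adverse event recording, a medication update, a physical examination and a local tolerance assessment at visit 1. The adverse event question in 11.2 is open. Section 10.4.3 sends new clinically significant findings after visit 0 to the adverse event page, and flow chart footnote a makes visit 0 the start of screening. A reaction that persists, was treated, or is remembered thus has a route into the data.

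Two limits apply. The local tolerance scale in 10.4.6 has no item for itching or swelling, which 5.2 gives as the commonest signs. A local sign becomes an adverse event under 10.4.6 only if dosing is stopped or the subject asks for it to stop, which cannot apply before dosing.

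**4. What is left**

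Two groups remain: men who attend visit 1 after a non-serious reaction that resolved and do not mention it, and men who are tattooed and never attend visit 1. For the second group, the applicable provisions are the screening log (8.5), serious event reporting (11.3) and insurer reporting (13.12). The log gives a reason for non-inclusion but is not an adverse event record.

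**5. Which order suits the imaging**

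Flow chart footnote e asks that a repeat tattoo be made at least 6 days before the next TrichoScan. Tattooing at visit 1 leaves 0 days to the visit 1 image and 2 days to a day 3 image. Tattooing at screening leaves 3 to 21 days to the visit 1 image. Screening is the better choice, although its shortest interval is still below 6 days.

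**The case against.** The strongest reply is that a date on which recording starts is not a cut-off for onset. Section 10.4.2 does not exclude events that began before visit 1, and an open question will often bring them out. Section 12.1.9 counts all adverse events separately from treatment-emergent ones, which suggests that pre-dose events are expected. The operational sections agree with one another, so sites would probably tattoo at screening in practice, after a check already listed first. Men refused because of a reaction would have that reason in the screening log.

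Most of this stands, and it narrows the gap to the two groups in step 4. It does not remove the contradiction. Nor does it answer 11.2 and 11.1.1, which read strictly exclude events before dosing.

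Three stronger readings are tempting and are not supported:

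- A reader might infer that tattoo reactions would be lost in all 60 enrolled men. The visit 1 procedures contradict this.
- A reader might take "The trial centres will screen a sufficient number of subjects (approximately n = 90) to include 60 eligible male subjects" to mean that 90 - 60 = 30 men would be tattooed for nothing. That assumes every screened man is tattooed, including those who fail the check listed before it. The protocol gives no such count.
- A reader might infer that men not enrolled are denied tattoo removal. Section 5.2 offers removal to the subject if the tattoo has not faded 3 months after trial end. It does not limit the offer to enrolled men, and the consent pages, which are not in the text reviewed, may settle the matter.

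**Conclusion.** The contradiction in timing is certain from the text. The recording gap is real but narrow: non-serious reactions that resolve and go unreported, plus tattooed men who never reach visit 1. It exists only if sites follow the screening order. It is widest if 11.2 and 11.1.1 are applied literally, and much smaller if 10.4.2 is read as including events since screening.

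The number of men affected cannot be derived from the protocol and is probably small. The risk to each man is also small: 5.2 describes bleeding as transient and nerve irritation as rare. No sample size, power or efficacy result depends on this. It is a minor point, worth making because the stated start of recording is later than the procedure whose risks 5.2 describes, and because correcting it costs almost nothing.

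**What to change.** 1. Keep the tattoo at screening and amend the synopsis and 7.1 to match. Consider applying the 6-day minimum of footnote e before the visit 1 image. That would narrow the screening interval from 3 to 21 days to 6 to 21 days.
2. State in 10.5.1 that only men who pass the screening inclusion and exclusion check are tattooed.
3. Start adverse event recording at the tattoo in the flow chart, 10.4.2 and 11.2. This also removes the conflict between 10.4.2 and 11.2 over the start date.
4. State in 11.1.1 that events caused by trial procedures count as adverse events.

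Optionally, state in 5.2 that the removal offer also covers men tattooed but not enrolled, unless the consent form already says so.

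The cost is wording, a flow chart edit and an adverse event entry open from screening. The change does not prevent every tattoo in a man who is later excluded, because serology may still be pending. It also does not by itself prompt a report from a man who never returns; it gives such a report a place in the record.
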